### **Concomitant Medication Assessment**

Use of medications (prescription or over-the-counter, including vitamins and herbal supplements) from the time of signing the consent through 30 days after last dose of study drug will be recorded in the eCRF at each study visit indicated in [Table 5](#).

During the Post-Treatment Period, antiviral therapies related to the treatment of HCV and medications prescribed in association with an SAE will be recorded in the eCRF at the visits indicated in [Table 6](#).

### **Assignment of Subject Numbers**

All screening activities must be completed and reviewed prior to enrollment. Subjects who meet the eligibility criteria will proceed to enrollment via the IRT system on Day 1 (Treatment Period).

Subject numbers will be unique 4-digit numbers and will begin with 1001 with the first two digits representing the investigative site, and the last two digits representing the subjects at that site. Enrolled subjects will keep their subject number assigned at the Screening Visit.

### **Study Drug Diary**

Subjects will be provided self-administration instructions and study drug diaries to record the exact date, time and number of tablets of study drug administration. On Study Day 1, the time of dosing will be recorded to the nearest minute by the site staff. The exact date, time and number of tablets of study drug taken will be recorded daily by the subjects between study visits. In the event the study drug diary is not available, the site may obtain dosing information via patient interview and record this information in the source notes.

### **Patient Reported Outcomes (PRO) Instruments (Questionnaires)**

Subjects will complete the self-administered PRO instruments (where allowed per local regulatory guidelines) on the study days indicated in [Table 5](#) and [Table 6](#). Subjects will be instructed to follow the instructions provided with each instrument and to provide the best possible response to each item. Site personnel shall not provide interpretation or assistance to subjects other than encouragement to complete the tasks. Subjects who are functionally unable to read or understand any of the instruments may have site personnel read the questionnaires to them. Site personnel will encourage completion of each instrument at all visits and will ensure that a response is entered for all items.

In this study, PRO instruments should be consistently presented so that subjects complete the SF-36v2 instrument first, followed by the EQ-5D-5L and followed by the HCVPRO. PRO instruments should be completed prior to drug administration (on Day 1) and prior to any discussion of adverse events or any review of laboratory findings, including HCV RNA levels.

#### **Short Form 36 – Version 2 Health Status Survey**

The SF-36v2 is a general Health Related Quality of Live (HRQoL) instrument with extensive use in multiple disease states. The SF-36v2 instrument comprises 36 total items (questions) targeting a subject's functional health and well-being in 8 dimensions (physical functioning, role physical, bodily pain, general health, vitality, social functioning, role emotional and mental health). Scoring is totaled into a Physical Component Summary and a Mental Component Summary. Higher SF-36v2 scores indicate a better state of health. Completion of the SF-36v2 should require approximately 10 minutes to complete.

#### **EuroQol-5 Dimensions-5 Level (EQ-5D-5L)**

The EQ-5D-5L is a health state utility instrument that evaluates preference for health status (utility). The 5 items in the EQ-5D-5L comprise 5 dimensions (mobility, self-care, usual activities, pain/discomfort, and anxiety/depression) each of which are rated on

5 levels of severity. Responses to the 5 items encode a discrete health state which is mapped to a preference (utility) using country-specific based weights, where available. Subjects also rate their perception of their overall health on a separate visual analogue scale (VAS). The EQ-5D-5L should require approximately 5 minutes to complete.

### **HCV Patient Report Outcomes (HCVPRO) Instrument**

The HCVPRO has been developed specifically to capture the function and wellbeing impact of HCV conditions and treatment. This instrument has been preliminarily validated and further validation is ongoing. The HCVPRO contains 16 items important to HCV patients; items are totaled to a summary score. Higher HCVPRO score indicates a better state of health. Completion of the HCVPRO should require approximately 5 minutes.

### **Study Drug Compliance for Kits**

Study drug compliance will be recorded per kit in the IRT system. Study drugs will be collected at each drug dispensation visit after Day 1, as indicated Section 5.5.6. The number of tablets of ABT-450/r/ABT-267, ABT-333, and of RBV remaining in each bottle will be recorded in the source and transferred to the IRT system along with the date of reconciliation.

### **HCV Genotype and Subgenotype**

Plasma samples for HCV genotype and subgenotype will be collected at Screening. Genotype and subgenotype will be assessed using the Versant® HCV Genotype Inno LiPA Assay, Version 2.0 or higher (LiPA; Siemens Healthcare Diagnostics, Tarrytown, NY).

### **HCV RNA Levels**

Plasma samples for HCV RNA levels will be collected as indicated in Table 5 and Table 6. Plasma HCV RNA levels will be determined for each sample collected by the

central laboratory using the Roche COBAS® AmpliPrep/COBAS® TaqMan® HCV Test v. 2.0. For this assay, the lower limit of quantification (LLOQ) is 15 IU/mL.

### **HCV Resistance Testing Sample**

A plasma sample for HCV resistance testing will be collected at 0-hour (prior to dose) and 2 hours post dose on Day 1 and at the study visits, indicated in [Table 5](#) and [Table 6](#). Specific instructions for preparation and storage of HCV RNA and HCV resistance samples will be provided by the central laboratory, the Sponsor, or its designee.

### **Archive Plasma Sample**

Archive plasma samples will be collected at the study visits, indicated in [Table 5](#) and [Table 6](#). Archive plasma samples are being collected for possible additional analyses, including but not limited to, study drug or metabolite measurements, viral load, safety/efficacy assessments, HCV gene sequencing, HCV resistance testing, and other possible predictors of response, as determined by the Sponsor.

Specific instructions for preparation and storage of archive samples will be provided by the central laboratory, the Sponsor, or its designee.

### **Archive Serum Sample**

Archive serum samples will be collected at the study visits, indicated in [Table 5](#) and [Table 6](#). Archive serum samples are being collected for possible additional analyses, including but not limited to, study drug or metabolite measurements, viral load, safety/efficacy assessments, HCV gene sequencing, HCV resistance testing, and other possible predictors of response, as determined by the Sponsor.

Specific instructions for preparation and storage of archive samples will be provided by the central laboratory, the Sponsor, or its designee.

### **Interferon Gamma-Induced Protein 10 (IP-10) Levels**

A plasma sample for IP-10 testing will be collected at the study visits indicated in [Table 5](#) and [Table 6](#). Specific instructions for preparation and storage of IP-10 samples will be provided by the central laboratory, the Sponsor, or its designee.

#### **5.3.1.2 Meals and Dietary Requirements**

All study drugs should be dosed together and administered with food, i.e., the AM dose of ABT-450/r/ABT-267, ABT-333 and RBV should be taken together with food and the PM dose of ABT-333 and RBV should be taken together with food.

#### **5.3.1.3 Blood Samples for Pharmacogenetic Analysis**

##### **IL28B Sample**

One (required) whole blood sample for DNA isolation will be collected from each subject Day 1 for Interleukin 28B (IL28B) pharmacogenetic analysis. This sample will not be used for any testing other than IL28B genotypes.

##### **Optional Sample for Pharmacogenetic Analysis**

A separate (optional) whole blood sample for DNA isolation will be collected on Day 1 (Treatment Period) from each subject who consents to provide the optional sample for pharmacogenetic analysis. If the optional pharmacogenetic sample is not collected at Day 1, it may be collected at any other visit during the study. The procedure for obtaining and documenting informed consent is discussed in [Section 9.3](#).

Specific instructions for preparation and storage of archive samples will be provided by the central laboratory, the Sponsor, or its designee.

Samples will be stored in a secure storage space with adequate measures to protect confidentiality. The samples will be retained while research on ABT-450, ABT-267 and ABT-333 (or drugs for the treatment of HCV) continues but no longer than 10 years.

## **5.3.2 Drug Concentration Measurements**

### **5.3.2.1 Collection of Samples for Analysis**

Blood samples for pharmacokinetic assay of ABT-450, possible ABT-450 metabolites, ABT-267, possible ABT-267 metabolites, ABT-333, ABT-333 M1 metabolite, other possible ABT-333 metabolites, as well as ritonavir and RBV will be collected by venipuncture at each study visit, including at Day 1, for the 0-hour and 2-hour PK sample collection. Intensive PK samples will be collected from at least 30 subjects at a visit on or after 2 weeks of the beginning of the treatment with DAAs. Samples will be collected at predose and approximately 2, 4, 6, and at 24 hours post DDA dose. Subjects may opt out of intensive PK sampling.

The date and time of the first dose of each drug will be recorded in the source documents and the eCRF. The time that each blood sample is collected will be recorded to the nearest minute.

### **5.3.2.2 Handling/Processing of Samples**

Specific instructions for collection of blood samples and subsequent preparation and storage of the plasma samples for the pharmacokinetic assays of ABT-450, possible ABT-450 metabolites, ABT-267, possible ABT-267 metabolites, ABT-333, ABT-333 M1 metabolite, other possible ABT-333 metabolites, ritonavir and RBV will be provided by the central laboratory, the Sponsor, or its designee.

### **5.3.2.3 Disposition of Samples**

The frozen plasma samples for the pharmacokinetic assays of ABT-450, possible ABT-450 metabolites, ABT-267, possible ABT-267 metabolites, ABT-333, ABT-333 M1 metabolite, other possible ABT-333 metabolites, ritonavir, RBV and archive plasma samples will be packed in dry ice sufficient to last during transport, and transferred from the study site to the central laboratory. Specific instructions for shipping to the analytical lab from the central laboratory will be provided by the central laboratory, the Sponsor, or its designee.

#### **5.3.2.4 Measurement Methods**

Plasma concentrations of ABT-450, ritonavir, ABT-267, ABT-333, ABT-333 M1 metabolite, and RBV will be determined using validated assay methods under the supervision of the Drug Analysis Department at AbbVie. Plasma concentrations of possible metabolites of ABT-450 and ABT-267, and other metabolites of ABT-333 may also be determined using non-validated methods.

#### **5.3.3 Efficacy Variables**

Virologic response will be assessed by HCV RNA in IU/mL at various time points from Day 1 through 48 weeks after completion of treatment.

##### **5.3.3.1 Primary Variable**

The primary endpoints are the percentage of subjects with SVR12 (HCV RNA < LLOQ 12 weeks after the last actual dose of study drug) and the percentage of subjects with SVR24 (HCV RNA < LLOQ 24 weeks after the last actual dose of study drug).

##### **5.3.3.2 Secondary Variable(s)**

The secondary endpoints are:

- The percentage of subjects with on-treatment virologic failure;
- The percentage of subjects with relapse by post treatment Week 12;
- The percentage of subjects with relapse by post treatment Week 24.

##### **5.3.3.3 Resistance Variables**

The following resistance analyses will be performed for subjects receiving study drugs who experience virologic failure (who have HCV RNA  $\geq$  1000 IU/mL):

1. the amino acid variants at baseline at signature resistance-associated positions identified by population nucleotide sequencing and comparison to the prototypic reference sequence,

2. the amino acid variants in available post-baseline samples identified by population nucleotide sequencing and comparison to the baseline sequence,
3. the amino acid variants in available post-baseline samples at signature resistance associated positions identified by population nucleotide sequencing and comparison to the prototypic reference.

#### **5.3.4 Safety Variables**

The following safety evaluations will be analyzed during the study: adverse event monitoring and vital signs, physical examination, ECG, and laboratory tests assessments.

#### **5.3.5 Pharmacokinetic Variables**

Values for the pharmacokinetic parameters of ABT-450, ABT-267, ritonavir, ABT-333, ABT-333 M1 metabolite, and RBV including the  $C_{\max}$ ,  $T_{\max}$ ,  $C_{\text{trough}}$ , and AUC will be determined by noncompartmental methods using data from subjects who participate in the intensive pharmacokinetic sampling. Additional parameters or summaries may be determined if useful in the interpretation of the data.

Individual plasma concentrations and pharmacokinetic parameters of ABT-450, ABT-267, ritonavir, ABT-333, ABT-333 M1 metabolite, ribavirin and possible metabolites of ABT-450, ABT-267, and ABT-333 (other than ABT-333 M1) will be tabulated and summarized.

#### **5.3.6 Pharmacogenetic Variables**

IL28B genotypes are associated with response to pegIFN/RBV. IL28B status will be determined for each subject and analyzed as a factor contributing to the subject's response to study treatment. These IL28B genotype results may be analyzed as part of a multi-study assessment of IL28B and response to ABT-450, ABT-267, ABT-333, or drugs of these classes. The results may also be used for the development of diagnostic

tests related to IL28B and study treatment, or drugs of these classes. The results of additional pharmacogenetic analyses may not be reported with the clinical study report.

Additional parameters or summaries may be determined if useful in the interpretation of the data.

DNA samples from subjects who separately consent for additional pharmacogenetic analysis may be analyzed for genetic factors contributing to the subject's response to study treatment, in terms of pharmacokinetics, pharmacodynamics, efficacy, tolerability and safety. Such genetic factors may include genes for drug metabolizing enzymes, drug transport proteins, genes within the target pathway, or other genes believed to be related to drug response (including IL28B). Some genes currently insufficiently characterized or unknown may be understood to be important at the time of analysis. Pharmacogenetic analyses will be limited to studying response to HCV therapy; no other analyses will be performed.

## **5.4 Removal of Subjects from Therapy or Assessment**

### **5.4.1 Discontinuation of Individual Subjects**

Each subject has the right to withdraw from the study at any time. In addition, the Investigator may discontinue a subject from the study at any time if the Investigator considers it necessary for any reason, including the occurrence of an adverse event or noncompliance with the protocol.

If, during the course of study drug administration, the subject prematurely discontinues during the Treatment Period or the Post-Treatment Period, the procedures outlined for the applicable Premature D/C Visit should be completed as defined in [Table 5](#) and [Table 6](#).

Ideally this should occur on the day of study drug discontinuation, but no later than 2 days after their final dose of study drug and prior to the initiation of any other anti-HCV therapy. However, these procedures should not interfere with the initiation of any new treatments or therapeutic modalities that the Investigator feels are necessary to treat the subject's condition. Following discontinuation of study drug, the subject will be treated in

accordance with the Investigator's best clinical judgment. The last dose of any study drug and reason for discontinuation from the Treatment Period will be recorded in the EDC (electronic data capture) system. The subject should then begin the Post-Treatment Period where the subject will be monitored for 48 weeks for safety, HCV RNA, the emergence and persistence of resistant viral variants and PROs.

If a subject is discontinued from study drug (Treatment Period) or the Post-Treatment Period with an ongoing adverse event or an unresolved laboratory result that is significantly outside of the reference range, the Investigator will attempt to provide follow-up until a satisfactory clinical resolution of the laboratory result or adverse event is achieved.

In the event that a positive result is obtained on a pregnancy test for a subject or a subject reports becoming pregnant during the Treatment Period, the administration of study drug (including RBV) to that subject must be discontinued immediately. Specific instructions regarding subject pregnancy can be found in Section 6.6. Subjects will be monitored for SVR in the Post-Treatment Period as described in Section 5.1.3. The Investigator is also encouraged to report the pregnancy information to the voluntary RBV Pregnancy Registry.

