### **Definition of Terms**

Non-responder	Received at least 12 weeks of IFN (alpha, bet or pegIFN) with RBV therapy for the treatment of HCV and failed to achieve undetectable HCV RNA (HCV RNA < LLOD) at the end of treatment
Relapser	Received IFN-based therapy (IFN [alpha, beta or pegIFN] with RBV therapy) for the treatment of HCV and was undetectable at or after the end of treatment, but subsequently had detectable HCV RNA within 24 weeks of treatment follow-up
IFN-based therapy (IFN [alpha, beta, or pegIFN] with RBV therapy) Intolerant	Treatment of HCV was discontinued during the treatment period due to intolerance to any of the components of the IFN RBV therapy.
Study Drug	ABT-450/r/ABT-267, ABT-333, RBV
Study Day 1	First day of study drug dosing
Treatment Period	Baseline/Day 1 through the day of last dose of study drug
Post-Treatment Period	Day after the last dose of study drug through Post-Treatment Week 48 or the day of Post-Treatment Discontinuation

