### **5.5 Treatments**

#### **5.5.1 Treatments Administered**

Each dose of study drug (ABT-450/r/ABT-267, ABT-333 and RBV) will be dispensed in the form of tablets at the visits listed in [Table 6](#).

ABT-450/r/ABT-267 will be provided by the Sponsor as 75 mg/50 mg/12.5 mg tablets. ABT 450/r/ABT-267 will be taken orally as 2 tablets once daily which corresponds to a 150 mg ABT-450/100 mg ritonavir/25 mg ABT-267 dose QD.

ABT-333 will be provided by the Sponsor as 250 mg tablets. ABT-333 will be taken orally as 1 tablet twice daily, which corresponds to a 250 mg dose BID.

RBV will also be provided by the Sponsor to the Investigator for use in this study. RBV will be provided as 200 mg tablets for Korea and Taiwan sites. RBV will be provided as 100 mg tablets for China sites. RBV has weight-based dosing 1000 to 1200 mg divided twice daily per local label. (For example, for Korea and Taiwan subjects weighing less than 75 kg, 200 mg RBV may be taken orally as 2 tablets in the morning and 3 tablets in the evening which corresponds to a 1000 mg total daily dose. Or for subjects weighing 75 kg or more, 200 mg RBV may be taken orally as 3 tablets in the morning and 3 tablets in the evening which corresponds to a 1200 mg total daily dose. For example, for Chinese subjects weighing less than 75 kg, RBV 100 mg tablets may be taken orally as five 100 mg tablets in the morning and five 100 mg tablets in the evening which corresponds to a 1000 mg total daily dose. Or for Chinese subjects weighing 75 kg or more, RBV 100 mg tablets may be taken orally as six 100 mg tablets in the morning and six 100 mg tablets in the evening which corresponds to a 1200 mg total daily dose.)

At Day 1 subjects will be administered study drugs by the study site personnel and receive instructions for self-administration of all study drugs from Study Day 2 through Study Week 12 of the Treatment Period.

On the day of intensive PK subjects will take their morning dose of DAAs and RBV onsite in the presence of study site personnel and the time of administration will be noted.

Subjects will be instructed to take study medication at the same time(s) every day. All compounds should be taken with food.

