## **6.6 Pregnancy**

Subjects and their partners should avoid pregnancy and males should avoid sperm donation throughout the course of the study, starting with Day 1 and for 7 months after the last dose of RBV (or per local RBV label) and/or consistent with local treatment guidelines for RBV.

Pregnancy in a study subject must be reported to AbbVie within 1 working day of the site becoming aware of the pregnancy. Subjects who report a positive pregnancy test during the Treatment Period must be notified to stop RBV immediately. Subjects will be monitored for SVR in the Post-Treatment Period as described in Section 5.1.3. Administration of DAAs may be continued at the investigator's discretion, if the benefit of continuing therapy is felt to outweigh the risk.

Information regarding a pregnancy occurrence in a study subject and the outcome of the pregnancy will be collected for pregnancies occurring up to 7 months (or per local RBV label) after the last dose of RBV for treatment with DAAs plus RBV. The investigator is encouraged to report the pregnancy information to the voluntary RBV Pregnancy Registry, if RBV is included within the regimen.

Subjects who discontinue study medications due to pregnancy will be monitored for SVR in the Post-Treatment Period as described in Section 5.1.3.

Pregnancy in a study subject is not considered an adverse event. However, the medical outcome of an elective or spontaneous abortion, stillbirth or congenital anomaly is considered a serious adverse event and must be reported to the Sponsor within 24 hours of the site becoming aware of the event.

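### On a positive pregnancy test during treatment, Protocol Section 5.4.1 orders all study drug stopped while Section 6.6 lets the DAAs continue, and neither section says which prevails

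*Protocol*

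**What the plan says.** Two sections of the Protocol deal with pregnancy in a subject on treatment.

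- **Section 5.4.1** (Discontinuation of Individual Subjects) covers a positive pregnancy test, or a pregnancy reported by the subject, during the Treatment Period. It states that "the administration of study drug (including RBV) to that subject must be discontinued immediately". It then adds: "Specific instructions regarding subject pregnancy can be found in Section 6.6".
- **Section 6.6** (Pregnancy) covers a positive test in the same period and states: "Subjects who report a positive pregnancy test during the Treatment Period must be notified to stop RBV immediately". Of the rest of the regimen it says: "Administration of DAAs may be continued at the investigator's discretion, if the benefit of continuing therapy is felt to outweigh the risk".

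The Definition of Terms in Section 1.2 gives study drug as "ABT-450/r/ABT-267, ABT-333, RBV". Section 5.5.1 uses the term in the same way: "Each dose of study drug (ABT-450/r/ABT-267, ABT-333 and RBV) will be dispensed in the form of tablets". Section 6.3 identifies the DAAs as the two products other than RBV.

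**The concern.** Section 5.4.1 is where a site looks to learn when a subject must come off drug, and Section 6.6 is where it looks for pregnancy. For two of the three products, the first section requires a stop and the second allows continuation. A positive test calls for immediate action, and the site should not have to decide at that moment which section governs.

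Participant safety is at stake. With approximately 18 sites in China, South Korea and Taiwan, the same event could be handled in different ways, with different fetal exposure to investigational drugs. Compliance is also affected. Under Section 7.0 an investigator may not depart from the protocol without the Sponsor's prior review and agreement, except to remove an immediate hazard. An investigator acting on one section could therefore be recorded as deviating from the other.

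**Working it through.** No arithmetic applies, because no alpha, power, rate or sample size in the Protocol depends on this point. The check is a comparison of the texts.

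**Step 1: is it the same event?** Section 5.4.1 is triggered by a positive test or a reported pregnancy in the Treatment Period. Section 6.6 is triggered by a reported positive test in the Treatment Period. The triggers overlap on a positive test during treatment, which Table 5 schedules at Weeks 4, 8 and 12 for women who need testing.

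**Step 2: does the Section 5.4.1 order reach the DAAs?** It does. Study drug is a defined term that includes both DAA products, and Section 5.5.1 uses it that way. The parenthesis in Section 5.4.1 that adds RBV makes sense only if more than RBV is meant.

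**Step 3: does Section 6.6 say something different about the DAAs?** It does. Only RBV is named as having to stop, and the DAAs may go on if the investigator judges the benefit to outweigh the risk.

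**Step 4: does the text settle precedence?** It does not. Section 5.4.1 refers the reader to Section 6.6 for specific instructions, but its own order is unconditional and makes no exception for the DAAs. Section 6.6 does not refer back to the order or qualify it.

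**Step 5: which actions bring out the conflict?**

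| Action at the site after a positive test | Section 5.4.1 | Section 6.6 |
|---|---|---|
| RBV and both DAA products stopped at once | Complies | Complies |
| RBV stopped at once, DAAs continued on a benefit-risk judgement | Breach | Permitted |
| RBV not stopped at once | Breach | Breach |

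The sections differ in the second row only. They agree that RBV stops immediately, and both provide for SVR monitoring in the Post-Treatment Period.

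**The case against.** The strongest reply is that Section 6.6 is the specific text and Section 5.4.1 sends the reader there, so a site that follows the document ends at one detailed section and there is no real conflict. The cross-reference does help, but it does not settle the matter. Specific instructions usually add detail to a general order. Here they would turn an unconditional requirement into a permission, and neither section says that this is intended. A site that acts on Section 5.4.1 without turning to Section 6.6 never sees the discretion.

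A second reply is that the rules are not opposites, and this stands in full. Section 6.6 permits the DAAs to continue; it does not require it. A reader might infer that a site cannot satisfy both sections, but the first row of the table shows that it can.

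A third reply is that the event will be rare. Inclusion criterion 7 requires two effective contraceptive methods during treatment for women of childbearing potential with male partners, and exclusion criterion 8 bars women who are pregnant or plan to be. This also stands. It limits how often the conflict can arise, but it does not tell a site what to do when it does.

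**Conclusion.** The contradiction is real and wrong as written, but narrow. It concerns the DAAs only, and only when an investigator chooses to continue them. Its importance comes from participant safety and from giving sites one instruction they can follow. The conclusion rests on the Protocol's own definition of study drug and on the absence of any statement of precedence. The Protocol gives no expected number of pregnancies, so no frequency is put on it.

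Two stronger readings are tempting and are not supported:

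- **That the conflict moves the SVR result.** One subject in about 100 carries one percentage point of the SVR rate, but that is the weight of a subject and not an effect of this contradiction. A different last-dose date does not by itself turn a response into a failure, and nothing changes if all drugs are stopped. No change in SVR12 or SVR24 has been shown.
- **That the anchor date for SVR is left undefined.** Section 5.3.3.1 times SVR12 and SVR24 from the last actual dose of study drug, and Sections 5.4.1, 5.5.6 and 5.5.7 provide for last-dose information to be recorded. The date follows from what the subject actually took, whichever rule was applied. Table 13 already provides for RBV alone to be interrupted, with possible discontinuation, so pregnancy does not raise a new timing problem.

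**What to change.** Reconcile Sections 5.4.1 and 6.6 into a single rule for the DAAs after a positive pregnancy test or reported pregnancy in the Treatment Period. State it identically in both places, with the same trigger and with the products named. The choice of rule belongs to those clinically responsible for the trial, and this review takes no position on it. No separate change to the SVR timing rules is needed for this point.

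The cost is a sentence or two in a protocol amendment, the ethics committee approval that Section 9.1 requires for amendments, and matching site-training text. The consent form is not among the documents at hand, so whether it needs to change cannot be judged here; it should be checked against the reconciled rule. Sample size, endpoints and analyses are unaffected.
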